4.1.3.5. DLT definition

A dose-limiting toxicity (DLT) is defined as a clinically significant adverse event graded according to the National Cancer Institute Common Terminology Criteria for Adverse Events (NCI CTCAE) v5.0, observed following the administration of the test drug, assessed as unrelated to disease progression, intercurrent illness, or concomitant medications, considered at least possibly related to the test drug by the investigator and that meets any of the criteria included in Table (4.1.3.5) 1.

For each patient, an assessment of DLT will be performed at the end of the first cycle of treatment, through C1D28. This assessment will include all toxicities observed starting from the LID period through C1D28. Only DLTs occurring during the LID period + Cycle 1 will be included in the Bayesian logistic regression model (BLRM) that estimates the relationship between dose and DLTs. However, monitoring for DLTs that occur after Cycle 1 will continue, in case there is evidence for delayed or cumulative toxicity.

Table (4.1.3.5) 1 - Toxicity criteria according to NCI CTCAE grading

TOXICITY	DLT CRITERIA
Eye disorders: blurred vision; cataract; corneal ulcer; dry eye; eye pain	Grade ≥ 3 confirmed by an ophthalmologic examination
GI disorders	Grade ≥ 3 nausea, vomiting or diarrhoea resulting in hospitalization, tube-feeding or use of total parenteral nutrition (TPN) Grade 4 diarrhoea
Renal abnormalities	Grade ≥ 3 serum creatinine
Hepatic abnormalities	AST or ALT ≥ 3 xULN along with a total bilirubin > 2.0 xULN and confirmed Hy's law cases according to FDA guidance; For patients with elevated baseline AST or ALT or total bilirubin: [AST or ALT > 2.0 xbaseline AND > 3.0 xULN] OR [AST or ALT > 8.0 xULN], whichever is lower, combined with [total bilirubin > 2.0 x baseline AND > 2.0 xULN] Isolated Grade 3 AST or ALT which does not resolve within 7 days to Grade ≤ 1 Isolated Grade 4 AST or ALT
For any Grade ≥ 3 hepatic toxicity which does not resolve within 7 days to Grade ≤ 1 level or baseline, an abdominal CT scan or hepatic echography must be performed.	
Pancreatic abnormalities	Grade ≥ 3 serum lipase and/or serum amylase Grade ≥ 3 pancreatitis
For any Grade 3 or Grade 4 pancreatic toxicity, which does not resolve within 7 days to Grade ≤ 1 level or baseline, an abdominal CT scan must be performed	

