Creatine kinase (CK) / Creatine phosphokinase (CPK)	Grade ≥ 3 serum CK/CPK Grade 3 isolated electrolyte abnormalities (i.e. those occurring without clinical consequence) not recovered with or without intervention, to Grade < 2 level within 72 hours

TOXICITY	DLT CRITERIA
Electrolyte abnormalities (including magnesium, calcium, phosphorus, etc.) clinically significant	Any Grade 4 electrolyte abnormality
Cardiac disorders	QTcF interval \geq 501 ms or increase of $>$ 60 ms from baseline on at least two separate ECG assessments (1 assessment = triplicate ECG) Asymptomatic, absolute decrease in LVEF of 10% or greater from baseline AND LVEF $<$ 50% Asymptomatic, absolute decrease in LVEF of 20% or greater from baseline Troponin increase $>$ 10xULN or a troponin increase consistent with the diagnosis of a myocardial infarction (Grade 3) Symptomatic congestive heart failure
Skin and subcutaneous tissue disorders	Grade \geq 3 rash
Haematological abnormalities	Grade 4 neutropenia and/or thrombocytopenia persisting for 28 days after the start of azacitidine dosing in a cycle of therapy in the absence of active AML ($<$ 5% blasts) or active MDS or myelofibrosis
Other AEs	Any Grade \geq 3 AE Single event or multiple occurrences of the same event that lead to a dosing delay of $>$ 7 days in a cycle may be considered to be DLT by the Investigators and the Sponsor, even if not Grade \geq 3 Failure to restart test drug administration at the same dose due to drug-related toxicity Failure to restart test drug administration at the same dose within one cycle (i.e. 28 days) of the first missed dose due to delayed recovery from drug-related toxicity Failure to initiate cycle 1 after completing the LID period or failure to receive LID2 after receiving the LID1, due to drug-related toxicity
NCI CTCAE v5.0 will be used for grading	

The following criteria will not be considered as DLT:

- Grade 3 nausea, vomiting, diarrhoea, anorexia or constipation that do not result in hospitalization, tube-feeding or use of TPN
- Grade 3 fatigue, asthenia, fever
- Grade 3 isolated electrolyte abnormalities (i.e. those occurring without clinical consequence) that resolve, with or without intervention, to Grade $<$ 2 level in 72 hours

Patients who meet any of the criteria included in Table (4.1.3.5) 2 at the end of Cycle 1 will not be evaluable for DLT and therefore will be replaced during the dose escalation phase I part of the study, but not in the expansion parts of the study.

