Table (4.1.3.5) 2 - Non evaluability criteria

Permanently discontinued treatment before C1D28 for reasons other than DLT
Did not undergo a DLT assessment at the end of Cycle 1
Did not receive the minimum exposure criteria i.e. minimum number of doses according to the dose administration schedule of both IMPs prescribed from study entry to DLTs assessment visit (end of Cycle 1 D28), unless treatment was stopped for a DLT - see Table (4.1.3.5) 3
If a patient received more than the assigned IMP doses from study entry to DLT occurrence during the DLT assessment period, non-evaluability criteria will be reassessed by Sponsor and investigator - see Table (4.1.3.5) 3

Table (4.1.3.5) 3 - Minimum number of S64315 and azacitidine doses to meet minimum exposure until the end of cycle 1

Schedule description	Minimum number of doses
S64315 during the 2-week LID period (LID1 on D-13 and LID2 on D-6)	2 out of 2
S64315 (D2, D9, D16 and D23 in 28-day cycle)	3 out of 4
Azacitidine (D1 to D7 in 28-day cycle)	5 out of 7

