8.2.1. Screening period and inclusion visit

Prior to the inclusion and after ICF signature, the clinical assessments will include:

- Medical, surgical and radiotherapy history
- Previous and concomitant treatments
- Complete physical examination (including examination of general appearance, skin, neck (including thyroid), eyes, ears, nose, throat, lungs, heart, abdomen, back, lymph nodes, extremities, vascular and neurological examination including sensory and motor evaluation functions)
- Clinical evaluation including vital signs (temperature, HR, BP), body weight, height, and ECOG PS within 7 days before the inclusion
- Laboratory tests: blood haematology with differential, blood biochemistry (fasted) blood coagulation, thyroid function, urinary analysis within 7 days before inclusion and available for inclusion and hepatitis markers within inclusion period
- Cardiac markers (limited to troponin only)
- Serum pregnancy test for female of childbearing potential within 7 days before inclusion and available for inclusion
- Cardiac function assessment performed by echocardiography or MUGA scan; GLS assessment will be recommended during echocardiography, whenever possible, as a means to follow left ventricular systolic dysfunction
- Chest X-Ray (CXR), a chest X-Ray performed prior to ICF signature but no more than 21 days prior to the first day of IMP administration is acceptable
- Triplicate ECGs (i.e. 3 ECGs within 10 min): see [Table \(8.2\) 2](#)

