 - beyond D2 (applicable for all patients with a risk of developing TLS according to the investigator's judgment): prior to each S64315 infusion (predose) and 2h, 4h, 8h, 24h±2h after each S64315 EoI

*Predose exams to be performed within 24h prior to S64315 C1D2 and 3 days prior to any other IMP administration

 - Triplicate ECGs: see [Table \(8.2\) 2](#)

If Day 9 administration is not performed, all scheduled assessments should be performed at the next S64315 infusion (2nd S64315 infusion in cycle 1).

Cycle 2 and cycle 3

- Clinical examination:
 - Vital signs (temperature, HR, BP): D1 azacitidine predose*, D2 S64315 predose* and EoI, D9 S64315 predose*, D16 S64315 predose*, D23 S64315 predose*
 - ECOG PS on D1 azacitidine predose*
 - Body weight on D1 azacitidine predose*
- Laboratory tests:
 - Blood haematology with differential and blood biochemistry: D1 predose*, D2 predose*, D9 predose*, D16 predose*, D23 predose*
 - Blood coagulation, thyroid function and urinary analysis on D1 predose*
 - Cardiac markers (including troponin, CPK-MB and BNP) #: D1 predose*, D2 predose*, D9 predose*, D16 predose*, D23 predose*

in case of any troponin increase observed after the two first S64315 infusions of cycle 1, it will be recommended to assess cardiac markers at 48h and 72h after S64315 EoI, and after each subsequent infusion (before discharge and beyond, if needed), on a regular basis according to investigator's judgment

 - TLS laboratory parameters monitoring (WBC, creatinine, phosphorus, calcium, potassium, uric acid, LDH), applicable for all patients with a risk of developing TLS according to investigator's judgment, prior to each S64315 infusion; 2h, 4h, 8h, 24h ± 2h, after each S64315 EoI
- * Predose exams to be performed within 3 days prior any IMP administration
- Pregnancy test for women of childbearing potential (serum or urine) on D1
- Triplicate ECGs: see [Table \(8.2\) 2](#)
- Cardiac function assessment performed by echocardiography or MUGA scan on D1 predose within 2 days prior to the IMP administration

Cycle 4 and beyond

- Clinical examination:
 - Vital signs (temperature, HR, BP) on D1 and D2 predose*
 - ECOG PS on D1 predose*
 - Body weight on D1 predose*
- Laboratory tests:
 - Blood haematology with differential and blood biochemistry: D1 predose*, D2 predose*, D9 predose*, D16 predose*, D23 predose*
 - Blood coagulation and urinary analysis on D1 predose*

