10.2.6. Dose proposed by the model

The dose allocation will start at the dose combination of 50 mg and 75 mg/m² respectively for S64315 and azacitidine.

A maximum of 6 DLT-evaluable patients may be initially enrolled at a dose level, and a minimum of 3 DLT-evaluable patients must be treated at a given dose level before a new higher dose level may be evaluated.

All available data on DLTs, assessed starting from the LID period to C1D28 will be used for updating the model. Before making a dose allocation decision, all patients from a cohort must:

- have been treated with LID1 and LID2, 3 out of 4 S64315 infusions and 5 out of 7 azacitidine injections or
- have had a DLT within the LID period or the first cycle

If a patient is not eligible for inclusion in the Dose-Limiting Toxicity Evaluable Set (DLTES), she/he must be replaced.

If a DLT occurred at LID1, the DLT will be considered as relative to 25 mg of S64315 in monotherapy. If a DLT occurred at LID2, the DLT will be considered as relative to 50 mg of S64315 in monotherapy. In that case, the patient will be replaced to ensure the minimal number of patients needed in the cohort at the full tested dose. Those DLTs will be considered for dose recommendation during the EoC meeting.

At any time during the study, if DLTs occur in the first 2 evaluable patients of a cohort (whether it happened during the LID period or cycle 1), the BLRM could be updated in order to re-evaluate the current dose level before enrolment of any additional patients in the cohort. Once each cohort of patients is completed, the dose recommendation by the model will be based on posterior summaries including the mean, median, standard deviation, 95%-credible interval, and the probability that the true DLT rate for each dose lies in one of the following categories:

- [0,16%) under-dosing
- [16%,33%) targeted toxicity
- [33%,100%] excessive toxicity

Following the principle of EWOC, after each cohort of patients, the dose combinations fulfilling the EWOC criterion (i.e. it is unlikely (<25% posterior probability) that the DLT rate at the dose falls in the excessive toxicity interval) will be identified by the model. A dose not fulfilling the EWOC criterion cannot be recommended.

In addition, admissible dose increments for the next cohort will not exceed 100% of the previous dose of S64315.

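### An asymptomatic LVEF fall is a DLT, but the first scheduled on-treatment scan is tied to cycle 2 dosing while the DLT count stops at C1D28, so such a DLT can be left out of the BLRM

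*Protocol*

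**What the plan says.** **What counts as a DLT.** Protocol Table (4.1.3.5) 1 has two asymptomatic LVEF criteria. One begins "Asymptomatic, absolute decrease in LVEF of 10% or greater from baseline AND LVEF" and adds a value below 50%. The other is an absolute fall of 20% or more.

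**When LVEF is measured.** Section 8.2.1 has a scan at inclusion. The lead-in and cycle 1 lists in section 8.2.2 contain none. The next is under cycles 2 and 3: "Cardiac function assessment performed by echocardiography or MUGA scan on D1 predose within 2 days prior to the IMP administration". The withdrawal scan in section 8.2.3 is done only if the previous one is more than three weeks old.

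**When a DLT counts.** Section 4.1.3.5: "This assessment will include all toxicities observed starting from the LID period through C1D28". Section 10.2.6: "All available data on DLTs, assessed starting from the LID period to C1D28 will be used for updating the model". Section 10.2.1 gives the same cut-off for the BLRM.

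**Who is evaluable.** Table (4.1.3.5) 2 excludes a patient who "Did not undergo a DLT assessment at the end of Cycle 1", and one below the minimum exposure. It does not mention LVEF. SAP section 2.1 repeats these criteria, and SAP section 3.4.1 counts patients with a DLT before the end of the first cycle.

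**The concern.** The cut-off is a calendar day, whereas the measurement that can reveal this DLT is tied to the actual start of cycle 2. By then a patient may have had six S64315 infusions (D-13, D-6, D2, D9, D16 and D23) with no scheduled LVEF measurement since inclusion. Sections 4.1.3.5 and 10.2 do not assign a scan taken just before cycle 2 to cycle 1. Because evaluability does not require an LVEF result, a patient can enter the BLRM as having no DLT before being re-imaged.

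This matters because cardiotoxicity was the dose-limiting toxicity of S64315 alone (section 2.2.2), and one stated aim of the lead-in is early detection of cardiac sensitivity (section 2.3.6). Cohorts are small, so one DLT carries weight in the overdose-control calculation.

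**Working it through.** **1. Day arithmetic.** Inputs are a 28-day cycle, a scan on C2D1 predose or in the two days before, and a cut-off at C1D28. If cycle 2 starts on day 29 + k, the permitted scan days are 27 + k, 28 + k and 29 + k. A scan counts if its day is 28 or earlier.

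| Delay k | Permitted scan days | Inside the window |
|---|---|---|
| 0 | 27, 28, 29 | 2 of 3 |
| 1 | 28, 29, 30 | 1 of 3 |
| 2 or more | 29 or later | 0 of 3 |

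Delays are foreseen. Section 6.1.2 allows a late cycle for haematological or renal toxicity, and Table (8.12) 2 has rules for recovery beyond 14 and 21 days.

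**2. Reproducing the protocol's model.** Inputs from Appendix 8:
- S64315 power prior: means (-0.092, -0.507), SDs (0.982, 0.694), correlation 0.705, reference dose 1400 mg.
- Azacitidine: log(α2) with mean -3.75 and SD 2.
- Interaction η: mean 0, SD 9.902. Check: ln(2)/1.96 × 1400/50 = 9.902.

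Formulas from section 10.2.2: logit(π1) = log(α1) + β1 log(d/1400); logit(π2) = log(α2); combination odds = exp(η d/1400) × (π1 + π2 − π1π2)/((1 − π1)(1 − π2)). A dose is admissible if P(DLT rate ≥ 33%) is below 25%. Six million prior draws were weighted by the binomial likelihood.

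| DLTs observed | Next dose in Appendix 8 Table (1.3) 1 | Stated P(overtox) | Recomputed |
|---|---|---|---|
| 0/5 at 50 mg | 100 mg | 0.0666 | 0.0675 |
| 1/5 at 50 mg | 100 mg | 0.2246 | 0.2219 |
| 2/5 at 50 mg | 25 mg | 0.2032 | 0.1937 |
| 0/5 at 50, 0/3 at 100 mg | 200 mg | 0.1312 | 0.1307 |
| 0/5 at 50, 1/3 at 100 mg | 100 mg | 0.1118 | 0.1096 |

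All five agree within one percentage point.

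**3. Effect of one omitted DLT.** These are recomputed probabilities of excessive toxicity.
- Cohort at 50 mg. Recorded as 1/5, 100 mg is admissible (0.222). Counted as 2/5, 100 mg (0.464) and 50 mg (0.286) both fail, and only 25 mg passes (0.194).
- Cohort at 100 mg after 0/5 at 50 mg. Recorded as 0/3, 200 mg is admissible (0.131). Counted as 1/3, 200 mg fails (0.350).
- Cohort at 200 mg after 0/5 and 0/3. Recorded as 0/3, 250 mg is admissible (0.062). Counted as 1/3, 250 mg fails (0.308).

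Not every omission matters: 0/5 and 1/5 at 50 mg both lead to 100 mg.

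**The case against.** **The text can be read the other way.** Section 4.1.3.5 also says "Only DLTs occurring during the LID period + Cycle 1 will be included in the Bayesian logistic regression model (BLRM", where the operative word is *occurring*. SAP section 4.2.1.5 measures a cycle up to the first intake of the next one, so a predose C2D1 scan still precedes cycle 2. A fall seen then arose under lead-in or cycle 1 dosing. SAP section 4.2.3.1 takes DLTs as the investigator reports them. This shows an ambiguity, but it does not displace the C1D28 limit in sections 4.1.3.5, 10.2.1 and 10.2.6. The SAP definition serves exposure calculations. Sites could count the same finding differently.

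**Other safeguards exist.** Cardiac markers are taken repeatedly in the lead-in and cycle 1 (section 8.2.5.3). Troponin elevation brings in echocardiography or MUGA (Table (8.12) 1) and, in defined cases, cardiac MRI (section 8.2.5.4). This narrows the gap to LVEF falls without a triggering signal or symptom. A patient who stops with only the inclusion scan will often qualify for a withdrawal scan, but section 5.8.2 lets that visit fall up to 28 days after the last dose.

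**The model does not decide alone.** A reader might infer that the dose rests only on cycle 1 DLTs. Section 10.2.1 adds a clinical assessment of all safety data, section 10.2.6 treats the model output as guidance, and section 4.1.3.7 adds the end-of-cohort meeting and prior DSMB review. These bodies can see a late LVEF finding. They do not put it into the calculation that bounds the admissible doses. The numerical rule for DLTs after cycle 1 (section 10.3.2) applies only to the expansion part, which SAP section 1.3 says will not be conducted.

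**Conclusion.** The point holds as a gap between the scan timing and the counting rule. Followed literally, the protocol can leave a lead-in or cycle 1 LVEF DLT out of the BLRM and out of the SAP's cycle 1 DLT count. One such omission can change the model's admissible doses. The day arithmetic assumes that the two-day allowance gives three permitted days, C2D1 included. The dose examples assume that one such event happens.

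Three stronger readings are not supported:
- *Any delay of cycle 2 puts the scan outside the window.* A one-day delay still leaves day 28. Exclusion is certain only from two days.
- *The DLT rate is biased low by a known amount.* Omission would push the count down, but the documents do not say how often such findings occur, so no size can be given.
- *A dose decision in this trial was wrong.* Nothing in the documents shows that. SAP section 1.3.1 says escalation was stopped jointly on model estimates and a global review of safety, PK, PD and activity data.

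Because escalation has stopped, what remains is the reporting of DLTs and the MTD, still part of the primary objective in SAP section 1.1, and any reuse of the design. The LVEF summaries in SAP section 3.4.7 would expose some of these cases. This is a wording correction worth making, not a fault that invalidates the plan.

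**What to change.** Reconcile protocol sections 4.1.3.5 (including Table (4.1.3.5) 2), 8.2.2, 10.2.1 and 10.2.6 with SAP sections 2.1 and 3.4.1 by stating two things:

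1. The LVEF result of the first scheduled on-treatment scan, if obtained before any cycle 2 IMP, is attributed to the lead-in and cycle 1 DLT assessment, the BLRM and the DLT table, whatever its calendar date.
2. A patient's DLT assessment closes only when that scan has been read.

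The wording should also say how to handle a patient who completes cycle 1 but never starts cycle 2, so that the withdrawal scan may be the first one after baseline.

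Leave the scan schedule unchanged. Re-anchoring the scan to the end of cycle 1 would move a cardiac monitoring time point. If cycle 2 were late, it would either lose the check before cycle 2 or need a second scan.

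For the report, the SAP should identify any DLT attributed to cycle 1 by this rule. It should also tabulate DLTs after cycle 1, which protocol section 10.4.4.2 plans and SAP section 3.4.1 does not count.

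The cost is text only, with no extra imaging. In a reused design the end-of-cohort meeting may wait some days for a delayed scan, and the LVEF observation window would differ slightly between patients.

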8.2.3. Withdrawal visit

- Clinical examination: vital signs (temperature, HR, BP), ECOG PS and body weight
- Laboratory tests: blood haematology with differential, blood biochemistry, blood coagulation and urinary analysis
- Pregnancy test for women of childbearing potential (serum)
- Triplicate ECGs: see [Table \(8.2\) 2](#)
- Cardiac function assessment performed by echocardiography or MUGA scan (only if the previous assessment was performed more than 3 weeks ago)

8.2.4. Post-withdrawal follow-up

After the withdrawal visit, a contact or telephone call will be done with the patients:

- every 3 months (± 15 days) from the WV, up to 6 months, except in case of consent withdrawal for the dose escalation phase I part
- every 3 months (± 15 days) from the WV, up to 12 months, except in case of consent withdrawal for the expansion phase II part

The following information will be collected:

- the patient's survival
- the date of first disease progression
- the first line of therapy administered after withdrawal and its starting date

8.2.5. Cardiac safety

8.2.5.1. Central ECG recording

In order to monitor the potential of S64315 infusion in combination with azacitidine to delay cardiac repolarisation, serial triplicate 12-lead ECGs (i.e. 3 ECGs within 10 min) will be performed for the measurement of the QT and QTc interval (correction according to Fridericia's formula). 12-lead ECG parameters with at least 3 to 5 QRS complexes for each lead will be evaluated by Core Reading Centre: HR, PR interval, QRS duration, QT interval, RR interval, corrected QT, using Fridericia's formula.

Three print-out ECGs will be produced with at least 6 complexes recorded for each. The ECG recordings will be centrally read by a CRO, specialised in cardiac monitoring. The CRO will provide a 12-lead digital recorder, will train and certify the centres in terms of equipment and will employ a trained independent cardiologist to read the ECGs.

At each time point described in [Table \(8.2\) 2](#), the triplicate 12-lead ECG will be obtained after resting for 10 min prior to the recordings and in supine position. Predose ECG should be collected:

- within 7 days prior to inclusion and results available for inclusion
- after azacitidine injection and before S64315 infusion on CxD2 (day of coadministration)
- with 24h prior to any other S64315 infusion

Detailed instructions on ECG recordings are provided in the ECG manual.

In the event that an ECG abnormality is observed, additional examinations could be performed at the discretion of the investigator (e.g. a blood sample for ionogram (Na, K, Cl) in case of QTc prolongation).

The management of the patient/the study treatment will be based on the local reading of the ECGs; all the ECGs will be sent by the site on a regular basis to the central reading CRO. The final analysis of the QTc values throughout the study will be based on the central reading analysis.

At inclusion visit

The mean QTc will be calculated for each triplicate ECG according to Fridericia's formula. If the mean QTc is > 450 ms in men or > 470 ms in women, then 3 other ECGs (in 10 min) should be repeated 3 h later. The mean QTc will be recalculated. If the abnormality is confirmed, the patient will not be included.

During the study

Triplicate ECGs will be carried-out at the time points defined in [Table \(8.2\) 2](#). The mean QTc will be calculated to detect a possible QTc prolongation. Toxicity grading of QTc interval prolongation is defined by the CTCAE v 5.0 as follows:

Table (8.2.5.1) 1 - Toxicity grading of QTc interval prolongation is defined by the CTCAE (v 5.0)

Grade	Definition
1	QTc 450 - 480 ms
2	QTc 481 - 500 ms
3	QTc \geq 501 ms on at least two separate ECGs
4	Torsade de pointes or polymorphic ventricular tachycardia or signs/symptoms of serious arrhythmia

In the event of prolongation of the QTc interval according to Fridericia's formula, management of treatments will be performed as explained in the [Table \(8.12\) 1](#).

The recommendations described in the [Table \(8.12\) 1](#) are not intended to supersede the clinical judgment of the investigator and the treating physician, who will determine the appropriate management for the patient. ECG abnormalities considered clinically significant by the investigator will be reported in the eCRF as adverse events.

